A Comparison of McGrath[®] MAC versus C-MAC[®] Videolaryngoscopes in Morbidly Obese Patients Undergoing Bariatric Surgery: A Randomized, Controlled Clinical Trial

*[name], Asst. [name] of Anesthesiology and Reanimation, Inonu University Medical Faculty, Malatya, Turkey

[name], Asst. [name] of Anesthesiology and Reanimation, Inonu University Medical Faculty, Malatya, Turkey

[name], Asst. [name] of Anesthesiology and Reanimation, Inonu University Medical Faculty, Malatya, Turkey

Address all correspondence to:

[name], Asst. [name] of Anesthesiology and Reanimation, Inonu University Medical Faculty, Malatya, Turkey

Mail: [contact]

[contact]

[contact]

A short title: McGrath vs C-MAC in Morbidly Obese Patients

Conflict of Interest:

The authors declare that they have no conflict of interest.

Funding Information:

None

Study Protocol

Protocol: This study was approved by the Local Ethics Committee. We conducted a prospective, randomized, controlled clinical study with 80 morbidly obese adult patients undergoing bariatric surgery from 8 September to 20 October 2018 at a university hospital. This study was prepared in accordance with the Consolidated Standards of Reporting Trials [9].

Study Participants: Our study participants (n = 80) were morbidly obese patients with American Society of Anesthesiology (ASA) scores of III who were aged 18–65 years old, had a BMI \geq 40 kg/m2, and were presenting for bariatric surgery at our hospital. All surgery patients meeting these criteria during the study period were interviewed before surgery to obtain written informed consent to participate in the study. Patients who were aged under 18 - over 65 years old, pregnant or who had a BMI \leq 40 kg/m2, an allergy to anesthetic drugs, uncontrolled cerebrovascular disease, or drug and alcohol addiction were excluded, as were all patients who refused written informed consent.

Preoperative Procedures: Preanesthetic evaluations were performed on all patients one day before surgery. Age, gender, height, weight, BMI, ideal body weight (IBW), ASA physical status, and type of surgery were recorded. On the day of surgery, patients were taken to the operating room without premedication. Standard monitoring procedures were used, including heart rate (HR), noninvasive blood pressure (NIBP), electrocardiogram (ECG), peripheral oxygen saturation (SpO2), mean arterial pressure (MAP), and body temperature monitoring by esophageal probe.

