General Anesthesia Protocol: A standardized general anesthesia protocol was administered to all patients. After preoxygenation (100% 4 L/min O2 for 3 min), patients were induced with propofol (1–2 mg/kg), rocuronium (0.8 mg/kg), and fentanyl (0.1 μ g/kg) via intravenous (IV) route at doses calculated according to IBWs. Mask ventilation and tracheal intubation using

either the McGrath MAC (blade size: 4) or C-MAC videolaryngoscopes (blade size: 4) were performed by an experienced anesthesiologist who had previously used both videolaryngoscopes successfully at least two years (more than 200 times). Also, tracheal intubations were performed by both videolaryngoscopes with the blade size 4 and using stylet in endotracheal tubes. End-tidal carbon dioxide (EtCO2) was continuously monitored after intubation. Tidal volume and ventilation rate were adjusted to maintain the EtCO2 partial pressure of arterial blood at 35–45 mmHg. Additional rocuronium was intermittently injected according to need based on Train of Four (TOF; Dräger AG, Lübeck, Germany) values. TOF responses were assessed by ulnar nerve stimulation and adductor muscle response. Additional fentanyl (0.1–0.2 μ g/kg) was titrated for analgesia, as needed, if HR and/or MAP increased by 20% above baseline during surgery. Anesthesia was maintained in both groups by desflurane inhalation in a 0.5 O2 oxygen-air mixture. Desflurane was discontinued with the beginning of skin sutures and fresh gas flow was changed to 4 L/min of oxygen. In patients who did not

experience complications during surgery, sugammadex (IV, 2–4 mg/kg; Bridion®, MSD, Greenville, USA) was then administrated to reverse residual muscle relaxation at the end of surgery.

Randomization: This study was planned as a randomized prospective study. Randomization was performed using MedCalc v. 16 statistical software for Windows (medcalc.com.tr). Eighty patients were randomly allocated to two groups: McGrath (n = 40) and C-MAC (n = 40) (**Figure 1.** Flow diagram). All patients received standard surgical procedures determined by the same team of surgeons with experience in gastroenterology surgery. Patient pneumoperitoneum pressure ranged from 10–12 mmHg and pneumoperitoneum levels ranged from 30–45 degrees. Surgical management of sleeve gastrectomy and gastric bypass surgeries was not changed in any way.

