Also demographic characteristics, comorbidities, and preoperative airway assessment, including each patient's Mallampati score (1–4), thyromental distance (cm), and mouth opening (cm), were recorded one day before surgery. HR, MAP, respiratory rate, and SpO2 were recorded at baseline before anesthesia (T₀), before intubation (T₁), 1 min after intubation (T₂), 2 min after intubation (T₃), 3 min after intubation (T₄), and 5 min after intubation (T₅). In addition, adverse events of tracheal intubation, including dental trauma, blood on blade, cuff burst, laryngospasm, bradycardia (HR < 65 beats/min), and hypoxemia (SpO2 < 90%), were recorded during the 15 min perioperative period. Hoarseness and sore throat were also recorded during the first 24 hours after surgery.

Sample Size: Statistical power analysis was performed based on a pilot study on 14 morbidly obese patients in our institution showing mean time to intubation of 45 ± 18.0 s [standard deviation (SD)] with the McGrath MAC. For power calculations (OpenEpi, Version 3), equal standard deviation for both groups was assumed. To show a difference of 12 s between the two groups and with an alpha of 0.05 and two tailed and a power of 80%, we calculated that a minimum of 36 patients per group should be included in this study. We ultimately included a total of 80 patients to allow for patient drop-out.

27.06.2018

Statistical Analysis:

Data were analyzed using the Statistical Package for the Social Sciences program (SPSS 22.0, IBM). The Kolmogorov-Smirnov normality test was used to test whether quantitative variables showed a normal distribution. As some patient preoperative and anesthetic characteristics were distributed abnormally, nonparametric statistics was used. Quantitative data are presented as mean or standard deviation and categorical data are shown as numbers or percentages. Continuous variables were compared between the groups using a Mann-Whitney U test. Categorical variables were summarized using frequencies and percentages, and were compared between the groups using a Chi-Square test or Fisher's exact test. A repeated measures ANOVA was used to compare hemodynamic data within each group, while an unpaired t-test was used for comparisons between the two groups. Results were evaluated at a 95% confidence interval at a significance level of p < 0.05.

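### The within-group repeated measures ANOVA names no reference time and, on the recorded schedule, mixes the effect of induction with the response to intubation; respiratory rate after paralysis is not a patient response

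*Combined protocol and SAP*

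**What the plan says.** The Outcome Measures section lists the patient's hemodynamic response during intubation among the secondary outcomes. The schedule that follows it gives six recording times: "HR, MAP, respiratory rate, and SpO2 were recorded at baseline before anesthesia" (T0), then "before intubation (T₁"), then 1, 2 and 3 minutes after intubation, and finally "5 min after intubation (T₅").

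The state of the patient at those times comes from two other sections. Under Preoperative Procedures, "patients were taken to the operating room without premedication". Under General Anesthesia Protocol, after preoxygenation, "patients were induced with propofol (1–2 mg/kg), rocuronium (0.8 mg/kg), and fentanyl", followed by mask ventilation and intubation. The same section says "Tidal volume and ventilation rate were adjusted to maintain the EtCO2 partial pressure of arterial blood at 35–45 mmHg".

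For the analysis, "A repeated measures ANOVA was used to compare hemodynamic data within each group", with an unpaired t-test between the groups. The plan does not list the times that enter the ANOVA, name a reference time, specify contrasts, or say which variables count as hemodynamic data. A more general sentence in the same section has continuous variables compared between groups by Mann-Whitney U test and makes no exception for respiratory rate.

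**The concern.** The outcome is the response to intubation. The series starts in an awake, unpremedicated patient, and the induction drugs are given before the laryngoscope is used. A test of no change over T0–T5 can therefore fail because of induction alone. If the result is reported as a response to intubation, the attribution is unsupported. If one arm reaches significance and the other does not, that contrast could be misread as a device effect.

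Respiratory rate raises a separate point. Once the relaxant has been given, the team delivers the breaths, first by mask and then at a rate adjusted to an EtCO2 target. A between-group test at T1–T5 would compare how patients were ventilated, not how they responded.

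**Working it through.** **The plan's own figure.** The documents compute nothing on this point. Their one calculated figure, the sample size, reproduces: 2 × [(1.960 + 0.842) × 18/12]² = 35.3, rounded up to 36 per group. It does not bear on this question.

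**Inputs.** From the documents: 40 patients per arm, six times, significance level 0.05. Assumed, because the documents give no hemodynamic figures: SD 12 or 15 units, equal correlation between times of 0.3 to 0.8, and an induction fall *d* that is complete by T1 and constant to T5, with no response to intubation. That T1 falls after induction is implied by the sequence of care, not stated.

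**Formula.** The means are 0 at T0 and −*d* at T1–T5, so the sum of squared deviations over the six times is *d*² × 5/6. The noncentrality of the one-way repeated measures F test is λ = 40 × (*d*² × 5/6) / [SD² × (1 − ρ)], on 5 and 195 degrees of freedom, with critical value 2.26. For *d* = 5, SD 12, ρ 0.3: λ = 833.3/100.8 = 8.27, and the rejection probability is 0.57.

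| Fall | SD | ρ | λ | Noncentral F | Simulation |
|---|---|---|---|---|---|
| 5 | 12 | 0.3 | 8.27 | 0.57 | 0.57 |
| 5 | 12 | 0.6 | 14.47 | 0.84 | 0.84 |
| 5 | 15 | 0.6 | 9.26 | 0.62 | 0.59 |
| 10 | 12 | 0.3 | 33.07 | 0.998 | 0.996 |
| 10 | 15 | 0.3 | 21.16 | 0.96 | 0.96 |
| 10 | 15 | 0.6 | 37.04 | 0.999 | 0.999 |
| 10 | 15 | 0.8 | 74.07 | 1.00 | 1.00 |

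The simulations used 3,000 runs per setting at SD 12 and 1,500 at SD 15, the latter with a Greenhouse-Geisser correction. At a fall of 5 the result depends strongly on the assumptions. The corners that were not simulated give, by the same formula, 0.37 (SD 15, ρ 0.3: λ = 833.3/157.5 = 5.29) and 0.99 (SD 12, ρ 0.8: λ = 833.3/28.8 = 28.94).

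**The same test without T0.** With no response to intubation, the T1–T5 test rejects in 4.1–5.7% of runs in every setting simulated. With a true response of 10 units after a fall of 15 (SD 15, ρ 0.6), it rejects in 99.8%, and the paired T1-to-T2 contrast in 99.7%.

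**Does the T0–T5 test also react to intubation?** Yes. With no induction fall and a response of 10 units it rejects in 100% of runs. A significant result is therefore compatible with either cause.

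**Between-group tests.** With the same induction fall in both arms and no device difference, the unpaired t-test at T2 rejects in 4.7–5.9% of runs.

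**The case against.** The strongest reply is that the plan never says the ANOVA spans T0–T5. That is correct: the span is inferred from the schedule. But no time is excluded and no reference is named, so it is the natural reading, and if it is wrong the plan still needs to say so. T1 is recorded, so T1-based contrasts can be made from the planned data. That makes the fix cheap, but it does not supply the missing specification.

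A reader might draw several stronger conclusions that the documents do not support:

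- *That the test says nothing about intubation.* It reacts to a real response as well as to induction. The fault is confounding.
- *That both arms are bound to be significant.* At a fall of 5 units, taking the arms as independent, both reject in only 0.57² = 32% to 0.84² = 71% of trials. Near certainty needs assumed falls of about 10 units or more.
- *That ventilator settings explain the HR and MAP results, or that respiratory rate is in the ANOVA.* The ANOVA sentence covers hemodynamic data. Respiratory rate enters through the general rule for continuous variables. At T1, ventilation would be by mask, so only the later readings can be called ventilator-set.
- *That the device comparison is biased.* Induction follows one protocol in both arms and randomization balances it on average, so the between-group t-tests keep their error rate.
- *That the plan intends to read within-arm significance as a device effect.* It does not say so. The risk lies in reporting.

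**Conclusion.** The point holds as a limited one. Read with the schedule, the within-group ANOVA does not isolate the secondary outcome it serves, because induction alone can make it significant. With no response to intubation, the T0–T5 test rejects in 57–84% of arms at a fall of 5 units in the simulated settings (SD 12 with correlation 0.3–0.6; SD 15 with 0.6). Over the full range of SD 12–15 and correlation 0.3–0.8, the formula widens this to 37–99%. At a fall of 10 units the rate is about 96–100%. Restricting the test to T1–T5 brings it back to about 5%.

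All these values rest on assumed SDs, correlations and falls, and on an induction effect that is complete and stable by T1. If drug effects continue to develop after T1, even a T1-based within-arm change is not purely a response to intubation, so the device question belongs to the randomized comparison.

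The respiratory-rate point needs no arithmetic: after paralysis the rate is chosen by the team. Neither point touches the primary outcomes, the sample size or the validity of the between-group t-tests. This is a worthwhile improvement to a secondary analysis, not a threat to the trial's main conclusion.

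**What to change.** In the Statistical Analysis section:

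- Define hemodynamic data and analyse HR, MAP and SpO2 within groups over T1–T5, with T2–T5 each contrasted against T1. State that T1 is taken after induction, if that is the case.
- Report the change from T0 to T1 separately, as the induction effect.
- Base any device claim on the between-group comparison, for example change from T1 or a group-by-time model over T1–T5, and not on one arm being significant while the other is not.
- Report respiratory rate descriptively at all six times, with no hypothesis tests after T0.

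The cost is a change of wording and a re-run on data already recorded. No patients or measurements are added. In the simulated case of a 10-unit response, the T1-based analysis still detects it in over 99% of runs.
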